Task sharing is supported by the World Health Organization (WHO), formalized in its guideline document, *OptimizeMNH* and reiterated in the Safe Abortion guidelines. Recommendations in this key guideline document are based on and supported by evidence obtained through systematic reviews of research--including qualitative and case studies--and programmatic experience. As shown in the figure in Appendix 1, the cadre of health provider and the contraceptive method in question are organized by four categories of guidance—*recommended*, *recommended with targeted monitoring and evaluation (M&E)*, *consider in the context of rigorous research*, and *recommend against*. The guidelines recommend provision of all methods: tubal ligation, vasectomy, intrauterine devices (IUDs), implants and injectables by associate clinicians and non-specialist doctors. However, limitations are placed on the methods that midwives, nurses, auxiliary midwives, auxiliary nurses and lay health workers may provide. For example, there are no restrictions on the provision of oral contraceptive pills and condoms (which are not shown in Appendix 1) by lay health workers, but the provision of tubal ligation, vasectomy and IUDs is recommended against; implants can be provided in the context of rigorous research; and provision of injectable contraception using standard syringes for intramuscular injections should be accompanied by targeted M&E. Currently, there are no guidelines for subcutaneous contraceptive injectables.

These recommendations are subject to revision if new evidence becomes available and meets WHO standards. WHO uses the GRADE (Grades of Recommendation Assessment, Development and Evaluation) approach to assess the quality of the evidence—one of the factors that contributes to the strength of the recommendation. Currently, the evidence supporting lay health worker provision of injectable contraception, while strong and bolstered by many pilot studies and programs worldwide, does not include a randomized controlled trial (RCT). An RCT constitutes the highest level of evidence in the WHO research framework; thus, a trial demonstrating that lay health workers can just as safely and effectively initiate injectable contraception as clinically-trained cadres of health providers could modify the recommendation of targeted M&E for intramuscular injections.

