### *Lady Health Visitors*

LHVs assigned to health facilities that correspond to the catchment areas of these LHWs, and who may in the normal course of their duties serve as their supervisors, will be eligible.

Study logistics, resources and need will determine if LHVs should be included in trainings for DMPA IM, but they will be required to attend trainings on SP, as that method will be new to both health cadres. It is particularly important that LHVs be trained on SP along with LHWs, not only to ensure consistency in training and knowledge for both cadres, but also to enable LHVs’ supervisory obligations to their charges providing SP. Jhpiego will certify that once trained, LHWs and LHVs are proficient in screening, counseling and administration of both forms of DMPA prior to interacting with DMPA clients.

Screening and counseling on the use of either type of DMPA has been simplified by WHO’s decision to employ the same medical eligibility requirements for both IM and SP formulations and to harmonize recommendations for the re-injection schedule and grace period (i.e., 2 weeks before the re-injection date or as late as 4 weeks after). Therefore, the only difference in service delivery will be the injection technique for DMPA IM and SP, as all other elements of method provision remain the same.

LHWs and LHVs selected to participate in the trial should not be the “cream of the crop”. To reflect the real-world context outside a trial setting, any provider who successfully completes Jhpiego’s training should be eligible to participate in the trial. Consent will be sought from LHWs and LHVs to observe their interactions with DMPA clients, including the provision of services, as well as to be interviewed by study staff.

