Given the relationship between LHWs and LHVs within clinics, we plan to account for the correlations of participant outcomes within providers and providers within clinics in the analysis. We expect that some of these correlations would lead to decreases in power, others to lead to increases in power for within

clinic comparisons. Power calculations were not adjusted for these potential correlations as the net effect on power may be offset with each other.

Please note that the screening outcome is not affected by the injection technique used, so power calculations focus on the overall comparison between LHV and LHW on the primary outcome. Furthermore, comparisons regarding injection techniques will be considered exploratory.

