IRBNET# 1035709: A randomized controlled trial of safety and effectiveness of Depo Provera intramuscular and subcutaneous administration comparing lay Lady Health Workers with clinically-trained Lady Health Visitors in Pakistan

STATISTICAL ANALYSIS PLAN

This statistical analysis plan gives a detailed explanation of the data analysis summary included in the study protocol.

I. Study Objectives

The goal of this evaluation is to assess whether the community health worker cadre, Lady Health Workers (LHWs) in Pakistan can screen and initiate women on intramuscular (IM) and subcutaneous Depo Provera injections as safely and effectively as their clinically-trained counterparts, Lady Health Visitors (LHV). Although LHWs are already allowed to provide follow-up doses in the community, this RCT will focus on the comparison of safety and effectiveness of screening, counseling and administration of DMPA IM and the subcutaneous injection, Sayana Press® (SP).

The study's primary outcomes are:

- Proportion of Lady Health Workers and Lady Health Visitors that appropriately screen women for DMPA use;
- Proportion of Lady Health Worker and Lady Health Visitor clients that report discussion with their respective providers on side effects, danger signs, advantages and disadvantages of DMPA use;
- Proportion of Lady Health Workers and Lady Health Visitors that demonstrate appropriate injection technique
- Proportion of Lady Health Workers and Lady Health Visitors that report needle stick injuries;
- Proportion of Lady Health Workers that properly maintains a client (re)injection log.

A secondary objective is to assess whether the clients of LHWs and LHV are equally satisfied with their respective providers and the family planning services they provide.

The study's secondary outcomes are:

- Satisfaction with the method;
- Satisfaction with the services received from the provider;
- Reports of client ability to speak freely and ask questions of provider;
- Friendly and respectful behavior toward client.

II. Study Design

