There are 15 screening questions on the job aid that providers use to determine if a client is or is not a good candidate for DMPA or needs further evaluation before initiating DMPA. The provider makes a global decision of eligibility or ineligibility based on the job aid items and whether or not she would subsequently initiate the client on DMPA. The observer notes the provider's decision whether to start the client on DMPA. This global decision (and not agreement on every screening item), is compared with the gold-standard nurse's assessment of client eligibility to generate the outcome variable for appropriate screening. Thus, the gold standard nurse's overall assessment of eligibility is made after the provider's assessment, and s/he is the final arbiter of eligibility. Thus, if the gold standard nurse determines that the client is eligible to use DMPA, the latter will receive the injectable regardless of the provider's assessment. To avoid bias, the gold standard nurse is blinded to the type of provider who assessed the client beforehand. Whether or not they are deemed eligible to use DMPA as their chosen method, all clients will receive counseling appropriate to their circumstance.

Counseling for DMPA use

Appropriate counseling is a composite binary variable that will be calculated from observations of the discussion between the provider and client. If the provider spoke to the client about side effects, warning or danger signs, advantages, and disadvantages of DMPA, then the conditions are met for appropriate counseling (all conditions must be met for considering the counseling appropriate). If any is missing, the counseling is deemed inappropriate. These variables will also be presented separately in the descriptive analyses by type of provider (and urban/rural setting if the data are not pooled).

Appropriate injection technique

Appropriate injection technique is assessed using checklists for DMPA-IM and DMPA-SC previously developed and validated for this purpose. To meet the criteria for appropriate administration of the injection, the provider must complete 80% of the items on the checklist (i.e., at least 18 out of 22 for SP and at least 14 out of 17 for IM).

D. Blind Data Review

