As part of the blind analysis review, we will ascertain whether or not study outcomes differ for rural and urban sites. If they do not differ, as anticipated, we will combine the data from the five sites in Karachi with the five sites in Thatta. If differences are detected via descriptive analyses, we will present stratified results, but will be unable to test for significant differences as the trial was not powered for that purpose. In that event, the focus will be on the urban sites only, whose sample size (n=342) was powered to test the non-inferiority hypothesis.

Other comparisons between groups will be primarily descriptive to explore the differences in the provision of DMPA services and client satisfaction measures by each cadre of provider, by DMPA type and urban/rural setting if those data are not pooled. Similarly, objective and provider-perceived comparisons between injection techniques and injection characteristics, respectively, will be primarily descriptive and exploratory.

Analyses by Objective

Objective 1: *To assess whether LHWs can screen and initiate women on DMPA injections as safely and effectively as LHV.*

To answer this objective, the analysis will report the odds ratio of appropriate screening and counseling by LHWs compared with LHV using multi-level generalized mixed models as described above. The generalized linear mixed model accounts for the multilevel structure of the data (i.e., clinics and providers).

Objective 2: *Assess whether DMPA clients of Lady Health Workers and Lady Health Visitors are equally satisfied with their respective providers and the family planning services they provide.*

Descriptive analysis will be completed using indicators of client satisfaction and client-provider interactions for LHW and LHV clients.

Table 2: Summary of analysis approach and data sources for the primary and secondary outcomes

Outcome	Analysis	Stratified by	Source
Objective 1 Outcomes			
Screening for DMPA use	GLMM and descriptive	Cadre, urban/rural	Observation checklist of screening and gold-standard nurse's assessment
Counseling/Discussion of DMPA side effects, danger/warning signs, advantages and disadvantages	GLMM and descriptive	Cadre, urban/rural	Observation checklist of screening
Appropriate injection technique*	Descriptive	Cadre, urban/rural	Observation checklist for DMPA-IM, q1-q17; Observation checklist for DMPA-SP, q1-q22
Needle stick injuries*	Descriptive	Cadre, urban/rural	LHW/LHV questionnaire

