Appropriate counseling defined as having discussed side effects, warning/danger signs, advantages, and disadvantages of DMPA				

Table 4: Comparison of Lady Health Workers and Lady Health Visitors on DMPA service delivery indicators (n, %)

	Urban	Rural		
	LHW	LHV	LHW	LHV
Appropriate screening				
Appropriate counseling				
side effects				
danger signs				
advantages/disadvantages				
Appropriate injection technique				
Needle stick injuries				
Client log maintained				

Objective 2: Client Satisfaction and Client-Provider Interaction

Table 5: Exemplar of Client Satisfaction and Client-Provider Interaction items (n, %)

	LHW		LHV	
	SP	IM	SP	IM
Satisfaction with method				
very satisfied				
somewhat satisfied				
not satisfied				
Satisfaction with services				
very satisfied				
somewhat satisfied				
not satisfied				
Satisfaction with provider				
very satisfied				
somewhat satisfied				
not satisfied				
Comfort asking questions				
yes				
no				

Figure 1: Graphic presentation of observation checklist for screening

Observation Checklist to Evaluate Providers Who Screen Clients for Initial DMPA Use

Type of provider being observed: Lady Health Worker
Lady Health Visitor

Please record the response given to the provider by the client for the following items. If the provider does not ask the question, please draw a line through the item.

NO	1. Have you ever been told you have breast cancer?	YES
NO	2. Have you ever had a stroke or heart attack, or do you currently have a blood clot in your legs or lungs?	YES
NO	3. Do you have a serious liver disease or jaundice (yellow skin or eyes)?	YES
NO	4. Have you ever been told you have diabetes (high sugar in your blood)?	YES
NO	5. Have you ever been told you have high blood pressure?	YES
NO	6. Do you have bleeding between menstrual periods, which is unusual for you, or bleeding after intercourse (sex)?	YES
NO	7. Have you ever been told that you have a rheumatic disease such as lupus?	YES
NO	8. Do you have two or more conditions that could increase your chances of a heart attack or stroke, such as smoking, obesity, high blood pressure, or diabetes?	YES
NO	9. Are you currently breastfeeding a baby less than 6 weeks old?	YES

If the client answered NO to *all of questions 1–9*, did the provider tell her she is a good candidate for DMPA?
Yes No
Did provider proceed to questions 10–15?
Yes No

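### SAP Table 2 and the Table 4 shell merge IM and SP injection technique, although the SAP text foresees a breakdown by DMPA type; a cadre deficit on one product would be halved in the merged figure

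*SAP*

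**What the plan says.** Both documents list "Proportion of Lady Health Workers and Lady Health Visitors that demonstrate appropriate injection technique" among the primary outcomes. SAP section V.C requires 80% of checklist items, which it gives as "at least 18 out of 22 for SP and at least 14 out of 17 for IM".

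SAP section VIII, Table 2 (the summary of analysis approach and data sources) names two sources for this outcome: "Observation checklist for DMPA-IM, q1-q17; Observation checklist for DMPA-SP, q1-q22". Its stratification entry is cadre and urban/rural. A footnote removes urban/rural if the data are pooled. The four satisfaction outcomes in the same table are stratified by cadre and DMPA type.

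The Table 4 shell, whose title begins "Comparison of Lady Health Workers and Lady Health Visitors on DMPA service delivery indicators (n", has one row for injection technique under urban and rural columns for each cadre. The Table 5 shell, for satisfaction, has separate SP and IM columns.

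The running text of SAP section VIII says: "Other comparisons between groups will be primarily descriptive to explore the differences in the provision of DMPA services and client satisfaction measures". It goes on to name cadre, DMPA type and, if not pooled, urban/rural setting as the breakdowns. The next sentence makes comparisons between injection techniques descriptive and exploratory.

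The protocol, under Lady Health Visitors, says that "the only difference in service delivery will be the injection technique for DMPA IM and SP". Under Sample size it adds: "Please note that the screening outcome is not affected by the injection technique used".

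**The concern.** The plan splits the satisfaction outcomes by product, but its tables merge the outcome that the protocol itself says differs by product. If urban and rural data are pooled, as the SAP anticipates, Table 2 calls for one technique figure per cadre, each mixing two procedures scored on two instruments.

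Objective 1 asks whether LHWs can initiate women on intramuscular and on subcutaneous DMPA as safely and effectively as LHVs. A merged percentage answers that for neither product. A shortfall on one would be diluted by the other, and opposite shortfalls could offset each other. One stated use of the trial is to "modify the recommendation of targeted M&E for intramuscular injections", and a figure half made up of subcutaneous injections does not speak directly to that.

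The missing result is LHW against LHV within each formulation. That is not the IM-against-SP comparison, which both documents set aside as exploratory.

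**Working it through.** **Pass marks.** 0.80 x 22 = 17.6, rounded up to 18 for SP. 0.80 x 17 = 13.6, rounded up to 14 for IM. Both match SAP section V.C, so one 80% rule is applied to two instruments.

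**Inputs.**
- Cadre allocation is 1:1 (protocol, Randomization procedures).
- The IM/SP randomization is described there as identical to the cadre one. I take this as an equal split, which is an assumption.
- Totals are 342 urban clients and about 442 overall (protocol, Sample size).
- Neither document gives expected rates for technique, so every rate below is assumed.

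**Dilution.** With the same product mix in both cadres and SP share w, the merged difference is (1 - w) x d(IM) + w x d(SP), where d is LHW minus LHV. At w = 0.5:

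| Assumed IM, LHW v LHV | Assumed SP, LHW v LHV | d(IM) | d(SP) | Merged |
|---|---|---|---|---|
| 95 v 95 | 90 v 95 | 0 | -5 | -2.5 |
| 95 v 95 | 85 v 95 | 0 | -10 | -5 |
| 95 v 95 | 80 v 95 | 0 | -15 | -7.5 |
| 85 v 95 | 95 v 85 | -10 | +10 | 0 |

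In the third row the LHW figure is (95 + 80)/2 = 87.5, against 95 for LHVs. If the SP share were 0.4 or 0.6, the merged difference there would be -6 or -9.

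**Cost in precision.** Four cadre-by-product cells give 442/4 = 110.5 clients each, or 342/4 = 85.5 for urban sites only. Taking one observed injection per client, the 95% half-width for a difference between two cells of size n is 1.96 x sqrt(2p(1 - p)/n). At an assumed p = 0.85, 2p(1 - p) = 0.255:

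- Per product, 442 clients: 1.96 x sqrt(0.255/110.5) = 0.094.
- Per product, 342 clients: 1.96 x sqrt(0.255/85.5) = 0.107.
- Merged, 442 clients (221 per cadre): 1.96 x sqrt(0.255/221) = 0.067.
- Merged, 342 clients (171 per cadre): 1.96 x sqrt(0.255/171) = 0.076.
- Rural only, unpooled, per product: about 100/4 = 25 per cell, and 1.96 x sqrt(0.255/25) = 0.198.

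These figures ignore clustering by provider and clinic, and they count every randomized woman as injected. Women found ineligible reduce the cells.

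**The case against.** **The text already provides for it.** SAP section VIII foresees comparisons of DMPA services by cadre and DMPA type, and its next sentence mentions injection techniques. Neither table forbids a split, and the data sit on separate checklists. This stands. A reader might infer a settled plan to report only merged results, but the documents do not support that. They show a mismatch between text and tables.

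**Both cadres start from a similar place.** LHWs are selected as already trained for follow-up IM doses, LHVs may give injectables without restriction, SP is new to both, and all must be certified proficient in both forms. Nothing here predicts opposite gaps, so cancellation is possible but not expected. The dilution of a one-product deficit needs no crossover and remains. The two cadres' preparation is also not fully parallel: LHVs must attend SP training, but whether they join IM training is left to logistics, resources and need.

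**Technique is not shown to be the only product-dependent primary outcome.** Needle stick injuries are also listed and could vary by device; the documents do not rule this out. The protocol supports only the narrower statement that technique is the service element that differs by product.

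**The policy aim is wider than IM.** A reader might take the IM recommendation as the sole target. The Introduction also names Pakistan's policies forbidding LHW initiation of DMPA, and wider community access through both products.

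**The outcome is descriptive.** It has no margin or test. This stands and limits the weight of the point.

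**Conclusion.** The point holds as an inconsistency within the SAP: the outcome's row in Table 2 and its row in the Table 4 shell omit the breakdown by DMPA type that the text foresees. Followed literally, the tables report a deficit confined to one product at half its size, given an equal IM/SP split, and opposite gaps could cancel. The -15 to -7.5 example rests on assumed rates and shows the mechanism; it does not forecast the result.

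A reader might infer that the trial's main conclusion is at risk. It is not. The trial is powered on screening, which the protocol says injection technique does not affect, so the non-inferiority test and the 342 stand. What is at stake is whether the descriptive evidence on technique can be read for each product.

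**What to change.** 1. In SAP Table 2, set the stratification for injection technique to cadre, DMPA type and urban/rural, with urban/rural dropped only if the data are pooled. DMPA type should be added, not substituted, because the SAP needs the urban/rural split if the data are not pooled.
2. In the Table 4 shell, replace the single row with a DMPA-IM row (14 of 17) and a DMPA-SP row (18 of 22), each with n/N by cadre.
3. State in section VIII that technique will be described separately for each formulation, so that text and tables agree.

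The edit is small and needs no new data. The cost is wider intervals: a half-width of about 9.4 instead of 6.7 points at 442 clients, or 10.7 instead of 7.6 at 342, on the assumptions above. Unpooled rural cells of about 25 women (near 20 points) would support counts and little more. Fixing the split in advance also avoids choosing it after unblinding.
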